9.4.2. Safety Monitoring

Lilly will periodically review evolving aggregate safety data within the study by appropriate methods.

For Phase 1a, safety data will be reviewed on a cohort by cohort basis. For Phase 1b, a safety review will be performed when every 10 patients have been treated for approximately 1 cycle for the first 20 patients enrolled into Phase 1b across all expansion cohorts, then every 3 months after the last patient enters study treatment (LPET) for 1 year, and then at least once a year afterward. The purpose of this Phase 1b safety review is to evaluate the safety and tolerability for each expansion cohort and determine if a dose-limiting equivalent toxicity (DLET) has been observed. For the first 20 patients enrolled into Phase 1b, based on mTPI-2 method, if 7 or more DLETs are observed, accrual will be temporarily paused, and the available data from Phase 1a and 1b will be analyzed to potentially modify the RP2D, or the study; considerations for stopping recruitment should be given after discussion with investigator and sponsor.

If a study patient experiences elevated alanine aminotransferase (ALT) $>5X$ upper limit of normal (ULN) and elevated total bilirubin (TBL) $>2X$ ULN, or ALT $\geq 8X$ ULN, liver tests ([Appendix 5](#)) should be repeated within 3 to 5 days including ALT, AST, TBL, direct bilirubin (D.TBL), gamma-glutamyl transferase, (GGT) and creatine phosphokinase (CPK) to confirm the abnormality and to determine if it is increasing or decreasing. If the abnormality persists or worsens, clinical and laboratory monitoring should be initiated by the investigator based on the hepatic monitoring tests ([Appendix 5](#)) and in consultation with the Lilly CRP/CRS. Monitoring of ALT, AST, and TBL should continue until levels normalize or return to approximate baseline levels.

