7.2.2. Dose Escalation: Phase 1a

7.2.2.1. Dose Escalation Method

Dose escalation of LY3415244 (at the levels shown in [Figure JZDA.5.1](#)) will be driven by a mTPI-2 method (Guo et al. 2016 [WWW]), taking into consideration available PK and pharmacodynamic data from previous dose levels. Each cohort in this study will contain a minimum of 3 patients.

Like the 3+3 design, the mTPI-2 method incorporates prespecified escalation rules. In contrast, the mTPI-2 method is based on quantitative models that incorporate uncertainty into the decision rules, thereby allowing more precise RP2D selection. If 3 or 6 patients are enrolled in a cohort, the escalation rule parallels a traditional 3+3 design. However, it allows flexible number of patients in a cohort. For example, with 2 DLTs per 6 patients enrolled, the mTPI-2 would recommend staying at the current dose, as analogy to 1 DLT per 3 patients enrolled in 3+3 design; therefore, it allows more patients for a more precise estimate of the DLT rate at this dose level.

[Appendix 7](#) provides the mTPI-2 escalation rules for any cohort size up to 20 patients.

Following a discussion between the Lilly CRP/CRS and the investigators, a more conservative dose selection may be applied to the next cohort (for instance, if PK/pharmacodynamic data suggest that further dose increase would not be expected to yield additional benefit). For example, if the rule indicates “E” to escalate, the dose may stay at the current dose level, be de-escalated to a lower level, or escalation may cease. In the mTPI-2, the cohort size is not fixed. However, each cohort in this study will contain a minimum of 3 patients, unless the escalation rules dictate that the dose should be de-escalated (“D” or “DU”). Doses can be escalated, de-escalated, and re-escalated following the rules in [Appendix 7](#). If the dose decision was “DU,” the dose cannot be re-escalated to that level.

This study is designed to identify a dose level with a dose-limiting target toxicity rate of 30%. The mTPI-2 method considers an equivalence interval (EI) around the target toxicity rate. For this study, the EI is elicited to be (25%, 35%), resulting in the rules in [Appendix 7](#).

Safety data, in particular DLTs, will be the primary criteria for the dose escalation. In addition, if available at the time of dose escalation decision, PK (for example, Cmax, AUC, pharmacodynamics results) will be used as secondary/supporting data for dose escalation.

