Appendix 6. Creatinine Clearance Formula

Note: This formula is to be used for calculating creatinine clearance (CrCl) from **local laboratory results only**.

For serum creatinine concentration in mg/dL:

$$\text{CrCl} = \frac{(140 - \text{age}^a) \times (\text{wt}) \times 0.85 \text{ (if female), or } \times 1.0 \text{ (if male)}}{72 \times \text{serum creatinine (mg/dL)}}$$

For serum creatinine concentration in $\mu\text{mol/L}$:

$$\text{CrCl} = \frac{(140 - \text{age}^a) \times (\text{wt}) \times 0.85 \text{ (if female), or } \times 1.0 \text{ (if male)}}{0.81 \times \text{serum creatinine} \text{ } (\mu\text{mo/L})}$$

^a age in years, weight (wt) in kilograms.

Reference: Cockcroft and Gault 1976.

Appendix 7. Dose-Finding Spreadsheet of the Modified Toxicity Probability Interval Method Showing Number of Patients Treated

		Number of Patients																			
		1	2	3	4	5	6	7	8	9	10	11	12	13	14	15	16	17	18	19	20
Number of DLTs	0	E	E	E	E	E	E	E	E	E	E	E	E	E	E	E	E	E	E	E	
	1	D	D	S	S	E	E	E	E	E	E	E	E	E	E	E	E	E	E	E	
	2		DU	D	D	D	S	S	S	E	E	E	E	E	E	E	E	E	E	E	
	3		DU	DU	D	D	D	S	S	S	S	E	E	E	E	E	E	E	E	E	
	4			DU	DU	DU	D	D	D	D	S	S	S	S	S	S	E	E	E	E	
	5				DU	DU	DU	DU	DU	D	D	D	D	D	S	S	S	S	S	S	
	6					DU	DU	DU	DU	DU	D	D	D	D	D	D	S	S	S	S	
	7						DU	DU	DU	DU	DU	D	D	D	D	D	D	D	D	D	
	8							DU	D	D	D	D									
	9								DU	D											
	10									DU											
	11										DU										
	12											DU									
	13												DU								
	14													DU							
	15														DU	DU	DU	DU	DU	DU	
	16															DU	DU	DU	DU	DU	
	17																DU	DU	DU	DU	
	18																	DU	DU	DU	
	19																		DU	DU	
	20																			DU	
E: Escalate to the next higher dose; S: Stay at the same dose; D: De-escalate to the previous lower dose; DU: De-escalate to the previous lower dose and the current dose will never be used again in the trial;																					

Source: Guo et al. 2016 [WWW].

The number of patients dosed at a given dose level is shown in the columns (X-axis), while the number of DLTs experienced is shown in the rows (Y-axis). The rules in this figure will be used for each dose level evaluated; the patient numbers and DLTs do not carry over from cohort to cohort. By locating the intersection of the number of patients dosed and the number of DLTs, 1 of 4 predefined rules is used:

- E: Escalate the dose
- S: Stay at the same dose
- D: De-escalate the dose

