- DU: De-escalate the dose due to unacceptable toxicity. The dose cannot be re-escalated to this dose level at a future point in the escalation.

For example, within a cohort:

- If 1 of 3 patients experiences a DLT, stay at the same dose (see “S” in column 3, row 1). The fourth patient must be treated at the same dose level.
- If 1 of 6 patients experiences a DLT, escalate the dose (see “E” at column 6, row 1).
- If 2 of 3 patients experience a DLT the dose to treat the next patient is de-escalated (see “D” at column 3, row 2).
- If 5 of 7 patients experience a DLT, the dose is determined to be unacceptably toxic, and the previous dose is defined as the MTD.

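### The Phase 1b pause trigger is the 20-patient mTPI-2 entry only, so 4 to 6 DLETs at the scheduled 10-patient review mandate no pause although Appendix 7 reads D or DU there

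*Protocol*

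**What the plan says.** Protocol Section 9.4.2 sets the review schedule for Phase 1b: "a safety review will be performed when every 10 patients have been treated for approximately 1 cycle for the first 20 patients", pooled across the four expansion cohorts. That gives one review at 10 patients and one at 20. The only numeric rule follows. It covers the first 20 Phase 1b patients and names mTPI-2 as its basis: "if 7 or more DLETs are observed, accrual will be temporarily paused". After a pause, Phase 1a and 1b data are analysed with a view to changing the RP2D or the study.

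The mTPI-2 settings are in Section 7.2.2.1: a 30% target and an equivalence interval, "For this study, the EI is elicited to be (25%, 35%), resulting in the rules in" Appendix 7. The same section says that the appendix "provides the mTPI-2 escalation rules for any cohort size up to 20 patients", so it has a column for 10 patients. The appendix defines DU as "De-escalate to the previous lower dose and the current dose will never be used again in the trial".

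SAP Section 5.12.2 (DLTs and DLT-equivalent toxicities) and SAP Section 5.18 (Interim Analysis) add no Phase 1b boundary.

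**The concern.** The rule names mTPI-2 as its basis and sits beside two scheduled looks, but its number belongs to the second look only. A first review that finds 6 of 10 patients with a DLT-equivalent toxicity meets no written trigger, while the cited table classes the same count as unacceptable toxicity. As written, the first review can force a pause only at an observed rate of 70% or more, against a 30% target.

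At stake is how early an RP2D that was set too high is caught. Protocol Section 10.1 requires as few as 3 Phase 1a patients at that dose, and Section 5.1.2 has all four expansion cohorts enrolling concurrently, so the 10-patient review is the first scheduled look at a larger sample.

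**Working it through.** **1. Reading Appendix 7.** The printed row for r DLTs has 21 − r entries, so it starts at n = r. This alignment agrees with the appendix's worked examples (1 of 3 = S, 1 of 6 = E, 2 of 3 = D, 5 of 7 = DU). The columns that matter are:

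| DLTs | n = 10 | n = 20 |
|---|---|---|
| 3 | S | E |
| 4 | D | E |
| 5 | D | S |
| 6 | DU | S |
| 7 | DU | D |

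**2. Reproducing the plan's own figure.** The decision is the subinterval of width 0.10, built around (0.25, 0.35), with the highest posterior density mass under Beta(1 + x, 1 + n − x). DU applies if P(rate > 0.30) > 0.95. The uniform prior and the 0.95 cutoff are assumptions, because the documents do not give them.
- n = 20: 6 = S and 7 = D. The stated trigger of 7 is reproduced.
- n = 10: 3 = S, 4 = D, 5 = D, 6 = DU. P(rate > 0.30) is 0.79, 0.92 and 0.978 for 4, 5 and 6 DLTs.

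These cells agree with the printed table. A few others differ under the assumed prior and cutoff (for example 3 of 8), but none is used here.

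**3. First review.** Let X ~ Binomial(10, p), where p is the true chance that a patient has a DLET by the review. The gap is P(4 ≤ X ≤ 6) = P(X ≥ 4) − P(X ≥ 7).

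| True rate p | Table says D or DU, P(X ≥ 4) | Written trigger met, P(X ≥ 7) | Gap |
|---|---|---|---|
| 30% | 35.0% | 1.1% | 34.0% |
| 40% | 61.8% | 5.5% | 56.3% |
| 50% | 82.8% | 17.2% | 65.6% |
| 60% | 94.5% | 38.2% | 56.3% |

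**4. Overall chance of a pause by patient 20.** Let Y ~ Binomial(10, p) be the DLETs in patients 11 to 20.
- Written rule: P(X + Y ≥ 7).
- Adding the 10-patient DU entry adds only the case X = 6, Y = 0. At p = 0.30 this is 0.0368 × 0.0282 = 0.0010.
- Adding both D and DU adds the sum over x = 4, 5, 6 of P(X = x) × P(Y ≤ 6 − x). At p = 0.30 this is 0.093.

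| True rate p | Written rule | Plus DU at 10 | Plus D and DU at 10 |
|---|---|---|---|
| 30% | 39.2% | 39.3% | 48.5% |
| 40% | 75.0% | 75.1% | 80.2% |
| 50% | 94.2% | 94.2% | 95.6% |
| 60% | 99.4% | 99.4% | 99.5% |

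**5. Delay or miss?** At a 40% rate, 5.2 of the 56.3 points in the gap (80.2 − 75.0) never reach seven DLETs by patient 20, about 9%. At 50% it is 1.4 of 65.6 points, about 2%. At a toxic dose, most gap cases are therefore paused later rather than not at all.

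**6. Length of the delay.** If DLETs are counted as they occur, the mean number of further patients until the seventh DLET after 6 of 10 is about 1/p: 2.5, 2.0 and 1.7 at 40%, 50% and 60%. This ignores reporting lag and later-cycle DLETs in the first 10 patients. If the count is read only at reviews, the pause waits for the 20-patient review. Section 9.4.2 does not say which applies.

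**The case against.** **The trigger is cumulative.** A reader might infer that at least 10 further patients must be dosed before a pause is possible. The text does not support that: it counts DLETs among the first 20 patients and does not tie the seven to the second review. After 6 of 10, the next DLET can pause accrual. This stands and limits the harm to a delay of uncertain length.

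**The sponsor can act anyway.** A reader might also infer that accrual has to continue at 6 of 10. It does not: no pause is mandated, but none is forbidden. The review's stated purpose is to assess safety, and Section 5.1 lets the RP2D change in Phase 1b on safety data. This stands too, but it does not explain why a rule said to rest on mTPI-2 uses one of two relevant columns.

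**An earlier boundary would not protect everyone.** Enrollment is concurrent and Section 9.4.2 states no hold, so some of patients 11 to 20 may already be dosed when the first review reads out. This stands.

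**Appendix 7 is a Phase 1a tool.** It counts Cycle 1 DLTs, whereas DLETs count in any Phase 1b cycle. Adding Phase 1a patients at the same dose could also change the entry: with 0 of 3 added, the table gives 4 of 13 = S and 6 of 13 = D. This weakens any claim that 6 of 10 settles the matter. But Section 9.4.2 itself carries mTPI-2 into Phase 1b, and its seven of 20 counts Phase 1b patients only, so the 10-patient column is the like-for-like comparison.

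**One cumulative boundary plus judgement is a legitimate design.** It is, if stated as such. The plan instead cites the table and is silent on its 10-patient entry.

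**Conclusion.** The concern holds as an inconsistency between Section 9.4.2 and Appendix 7. The 10-patient review has no boundary of its own, and counts of 4 to 6, which the cited table marks D or DU, mandate no pause. At true rates of 40% to 60% the first review lands in that gap 56% to 66% of the time. The consequence is chiefly a later pause, not a missed one, because the written rule already pauses by patient 20 with chance 75% to 99%.

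The entries come from the printed table and do not depend on the assumed prior or cutoff. The probabilities assume independent patients, a common DLET rate, at most one counted DLET per patient, and DLETs known at the review. How many patients are dosed during the delay cannot be fixed from the documents, since they do not say whether the count is checked continuously or only at reviews.

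**What to change.** Reconcile Section 9.4.2 with Appendix 7 so that the 10-patient review uses a boundary consistent with the Appendix 7 entry for the number of patients treated. In the same sentence, state that the count is patients with at least one DLET (Section 9.4.2 counts DLETs, while the appendix examples count patients), and whether it is checked continuously or only at the two reviews.

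Which entries should lead to a pause is for the sponsor to weigh. At a 30% rate, honouring only the 10-patient DU entry moves the overall chance of a temporary pause by patient 20 from 39.2% to 39.3%. Honouring D and DU moves it to 48.5%, in exchange for an earlier pause at higher rates. The change is a short amendment to one section and needs no extra patients, visits or data.

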9.4.2.1. Special Hepatic Safety Data Collection

Hepatic data, such as lab tests (see [Appendix 5](#)), liver related signs and symptoms, results from hepatic monitoring procedures, and liver biopsy assessment if available, should be collected in the event that a patient meets one of the following conditions during the course of the study:

- elevation of serum ALT to $\geq 10X$ ULN
- patients without liver tumors or liver metastasis: ALT $\geq 5X$ ULN and TBL $\geq 2X$ ULN
- patients with liver tumors or liver metastasis: ALT $\geq 8X$ ULN and TBL $\geq 2X$ ULN
- discontinuation from treatment due to a hepatic event or abnormality of liver tests
- occurrence of a hepatic event considered to be a SAE

9.5. Pharmacokinetics

Pharmacokinetic samples will be collected as shown in [Appendix 4](#).

Blood samples will be used to determine the study drug concentrations of LY3415244 (also known as bioanalytical samples).

Bioanalytical samples collected to measure LY3415244 plasma concentration will be retained for a maximum of 1 year following last patient visit for the study.

Instructions for the collection and handling of bioanalytical blood samples will be provided by Lilly. The actual start and end date and time of LY3415244 infusion must be recorded on the eCRF. The actual date and time that each bioanalytical blood sample is drawn must be recorded on the laboratory requisition page after the sample is drawn.

All study drug concentrations in bioanalytical plasma samples will be measured using validated assay methodology in a laboratory designated by Lilly.

The remaining sample collected for PK testing may be pooled and used for exploratory metabolism or bioanalytical assay validation work as deemed appropriate.

9.6. Pharmacodynamics

Pharmacodynamic samples will be collected as shown in [Appendix 4](#) to assess target engagement and activity for LY3415244. Potential pharmacodynamic markers may include measuring soluble markers (sPD-L1 and sTIM-3) in serum and immune cell subsets characterization and distribution. Tumor tissue, plasma, serum, and whole blood may be used for additional exploratory PD work as deemed appropriate by Lilly (see also Section [9.8](#)). Samples collected to measure pharmacodynamic biomarkers will be identified by the patient number (coded) and retained at a facility selected by the Lilly for a maximum of 15 years following last patient visit for the study.

9.6.1. Immunogenicity Assessments

Blood samples for immunogenicity testing will be collected as shown in [Appendix 4](#) to determine antibody production against LY3415244. Immunogenicity will be assessed by a validated assay designed to detect ADAs in the presence of LY3415244. Antibodies may be further characterized and/or evaluated for their ability to neutralize the activity of LY3415244.

In the event of a drug hypersensitivity event (immediate or non-immediate), additional samples will be collected as close to the onset of the event as possible and at 4 and 12 to 16 weeks after the event. Instructions for the collection and handling of blood samples will be provided by Lilly. The actual date and time (24-hour clock time) of each sampling should be recorded.

Samples will be retained at a facility selected by Lilly for a maximum of 15 years after last the patient visit for the study, or for a shorter period if regulations and ethical review boards (ERBs)/institutional review boards (IRBs) impose shorter time limits. The duration allows Lilly to respond to future regulatory requests related to LY3415244. Any samples remaining after 15 years will be destroyed.

9.7. Genetics

9.7.1. Whole Blood Sample for Pharmacogenetic Research

A whole blood sample will be collected for pharmacogenetic analysis as specified in [Appendix 4](#), where local regulations allow.

Samples will not be used to conduct unspecified disease or population genetic research either now or in the future. Samples will be used to investigate variable response to LY3415244 and to investigate genetic variants thought to play a role in cancer. Assessment of variable response may include evaluation of AEs or differences in efficacy.

All samples will be coded with the patient number. These samples and any data generated can be linked back to the patient only by the study site personnel. Samples will be retained at a facility selected by Lilly for a maximum of 15 years after the last patient visit for the study, or for a shorter period if local regulations and/or ERBs/IRBs impose shorter time limits. This retention period enables use of new technologies, response to questions from regulatory agencies, and investigation of variable response that may not be observed until later in the development of LY3415244 or after LY3415244 becomes commercially available.

Molecular technologies are expected to improve during the 15 year storage period and therefore cannot be specifically named. However, existing technologies include whole genome and exome sequencing, genome-wide association studies, multiplex assays, and candidate gene studies. Regardless of the technology utilized, data generated will be used only for the specific research scope described in this section.

9.8. Biomarkers

Biomarker research is performed to address questions of relevance to drug disposition, target engagement, pharmacodynamics, mechanism of action, variability of patient response (including safety), and clinical outcome. Sample collection is incorporated into clinical studies to enable examination of these questions through measurement of biomolecules including DNA, RNA, proteins, lipids, and other cellular elements.

As part of Lilly's ongoing efforts to understand the relationship between cancer, genetics, and response to therapy, this study will analyze systemic and tumor tissue-associated biomarkers relevant to LY3415244, mechanism of action of LY3415244, the variable response to study drug(s), immune function, and pathways associated with cancer, including solid tumors and 4 expansion cohorts (NSCLC, urothelial carcinoma, mesothelioma, and melanoma). These samples may also be used to develop related research methods or to validate diagnostic tools or assays.

Samples for biomarker research will be collected as specified in [Appendix 4](#), where local regulations allow. It is possible that biomarker data for patients in the study has already been generated from samples that were collected and analyzed prior to enrolling in this study. This may include data generated from genetic analyses. If available, these data may be requested from medical records for use in the research described in Sections [9.7.1](#), [9.8.1](#), and [9.8.2](#).

9.8.1. Tissue Samples for Biomarker Research

Tissue samples for biomarker research will be collected for the purposes described in Section 9.8. The following samples for biomarker research will be collected as specified in [Appendix 4](#), where local regulations allow.

Collection of the following tumor tissue sample(s) is **required** for all patients in order to participate in this study:

For patients participating in Phase 1a and Phase 1b (all cohorts):

- a newly obtained core or excisional pre-treatment biopsy of a tumor lesion **and**
- a tumor tissue sample from a newly obtained biopsy specimen collected during the study treatment period as shown in [Appendix 4](#).
- an archival formalin-fixed paraffin-embedded tumor tissue obtained from the primary tumor site, if available and not restricted by local regulations. (Regardless of whether or not the archival tissue is submitted, patients are still required to undergo pretreatment and on-treatment biopsies).

An attempt to obtain 4 core-needle biopsies or a surgical biopsy is required, unless medically contraindicated and discussed with Lilly CRP/CRS. Optimally, biopsies should be taken from the same lesion and from areas not previously irradiated. Biopsies should not be taken from areas that have been previously irradiated, unless the previously irradiated area has progressed.

Collection of the following tumor tissue sample(s) is **optional** for all patients participating in this study:

For patients participating in Phase 1a and 1b (all cohorts)

- a tumor tissue sample from a newly obtained biopsy specimen collected after disease progression or at additional study time points, if warranted and agreed upon by the investigator and Lilly. Such additional biopsies are optional and should be performed only if clinically feasible. If these additional samples are requested, they will be used to further investigate biomarkers that may explain treatment response and resistance mechanisms. If a biopsy is performed after the patient signs the ICF, Lilly may request a tissue sample from the biopsy for additional biomarker testing at any time during the study including post-progression.

Newly acquired tumor biopsies are requested because they provide the most current biomarker characteristics of the tumor compared with biopsies taken at the time of diagnosis (tumor characteristics may shift during subsequent lines of treatment). Pre- and on-treatment assessments are critical for meaningful clinical data; paired biopsies are planned to be tested from baseline over time for changes in molecular markers to document any potential immunomodulatory activity of treatment with LY3415244 and should be performed if clinically feasible. A minimum paired sample size of 19 in total is expected to provide adequate precision to estimate the immune response. Samples will be examined for biomarkers as described in Section 9.8, including but not limited to, TIM-3 and PD-L1 expression by immunohistochemistry.

The tissue samples should be obtained using an appropriate method. Tumor tissue should be submitted as a newly acquired excisional or core needle (minimum 18 gauge) or surgical biopsy in formalin. Cytological or fine-needle aspiration specimens are not acceptable. If additional tumor biopsies are collected as part of clinical care, they should be submitted, along with pathology reports, for further analysis. See the Laboratory Manual for details regarding sample handling. At the time of tissue collection process, due diligence should be used to make sure that the tumor sample (not a normal adjacent tissue sample or a tumor margin sample) is provided and contains tumor cells prior to shipment to the central laboratory. This will help ensure that a quality biopsy sample has been taken. The pathology report must be coded with the patient number. Personal identifiers, including the patient's name and initials, must be removed from the institutional pathology report prior to submission. Tissue samples collected on-study will not be returned.

Samples will be retained at a facility selected by Lilly for a maximum of 15 years after the last patient visit for the study, or for a shorter period if local regulations and/or ERBs/IRBs impose shorter time limits. This retention period enables the use of new technologies, response to questions from regulatory agencies, and investigation of variable response that may not be observed until later in the development of LY3415244 or after LY3415244 becomes commercially available.

Technologies are expected to improve during the 15-year storage period and therefore cannot be specifically named. Existing approaches, including but not limited to mutation profiling, copy number variability analysis, gene expression assays, multiplex assays, and/or immunohistochemistry may be performed on these tissue samples to assess potential associations between these biomarkers and clinical outcomes.

